FEV1	Forced Exhaled Volume in 1 second
FVC	Forced Vital Capacity
GCP	Good Clinical Practice
HIPAA	Health Insurance Portability and Accountability Act of 1996
ICH	International Conference on Harmonisation
IEC	Independent Ethics Committee
IRB	Institutional Review Board
MAUDE	Manufacturer and User Facility Device Experience
MEP	Maximum expiratory pressure
MIP	Maximum inspiratory pressure
MV	Mechanical ventilation
NMES	Neuromuscular electrical stimulation
PEF	Peak expiratory flow
PI	Principal Investigator
PTPdi	Pressure-time products of the diaphragm
PTPga	Pressure-time products of the gastric space
SAE	Serious adverse experience
SBT	Spontaneous breathing trial
SCI	Spinal Cord Injury
SPO2	Peripheral capillary oxygen saturation
VAP	Ventilator acquired pneumonia

2 Protocol Synopsis

TITLE	Breath synchronized Abdominal Muscle Stimulation to Facilitate Ventilator Weaning: A Pilot Study
SPONSOR	Liberate Medical, LLC
FUNDING ORGANIZATION	Liberate Medical, LLC
NUMBER OF SITES	1
RATIONALE	
In the U.S. over 500,000 patients have difficulty weaning from mechanical ventilation every year. These patients cost the health care system \$16 billion annually and have an increased risk of medical complications and morbidity.
 
A major factor responsible for weaning failure is the imbalance between decreased respiratory muscle strength and excessive respiratory load. VentFree (Liberate Medical, LLC) is an investigational device that applies electrical stimulation to the abdominal muscles in synchrony with exhalation. This is hypothesized to improve the strength of the respiratory muscles. The long term goal of this project is to determine whether this approach can reduce the number of days taken for patients to wean from mechanical ventilation.

STUDY DESIGN	This is a single center, participant blinded randomized placebo controlled pilot trial.
PRIMARY OBJECTIVE	The primary objective of this study is to determine whether NMES applied to the abdominal wall muscles in synchrony with exhalation can increase the strength of the respiratory muscles in prolonged mechanical ventilation patients
SECONDARY OBJECTIVES	The secondary objectives of the study is to evaluate whether this intervention also affects: (1) the thickness of the abdominal wall muscles and the diaphragm, (2) functional respiratory measurements, and (3) weaning outcome
NUMBER OF PARTICIPANTS	Twenty six: 13 in the treatment arm and 13 in the control arm.
PARTICIPANT SELECTION CRITERIA	
Inclusion Criteria:
 
 • Patients who have been mechanically ventilated for at least fourteen days. • Clinically stable: oxygen saturation > 90% with a fractional inspired oxygen ≤ 0.40, external PEEP ≤ 5 cm H₂O, temperature ranging from 35.5 to 38.5°C, no intravenous administration of vasoactive agents. 
Exclusion Criteria:

	
 Patients in whom Neuromuscular Electrical Stimulation (NMES) does not elicit a palpable contraction of the abdominal muscles. Patients with broken or irritated skin on the abdominal wall Patients with a history of neuromuscular disease Body Mass Index (BMI) $> 35 \text{ kg/m}^2$ Patients who are not medically stable Patients with a pacemaker Female patients who are pregnant Patients under the age of 18 Patients who are expected to die within four weeks Patients who are unable to follow verbal instructions Patients with epilepsy Patients with an abdominal wall hernia Patients with anoxic encephalopathy Patients with history of, or active, substance abuse
ACTIVE DEVICE	VentFree prototype (VF03) that delivers electrical stimulation pulses to the abdominal muscles during exhalation with a frequency of 30 Hz, a pulse width of 350 μs and 90% of the maximum current that the participant can tolerate. These stimulation parameters were selected to cause a tetanic (continuous) contraction of the abdominal muscles, without pain for the patient. Stimulation will be administered for 30 minutes 2 times per day, 5 days per week, for 6 weeks; or until the patient is weaned from mechanical ventilation.
CONTROL DEVICE	Modified VentFree prototype (VF03) that delivers stimulation pulses to the abdominal muscles during exhalation with a frequency of 10 Hz, a pulse width of 100 μs and current set to 10 mA. These stimulation parameters were chosen to cause a twitch contraction of the abdominal wall muscles. Stimulation will be administered for 30 minutes, 2 times per day, 5 days per week, for 6 weeks; or until the patient is weaned from mechanical ventilation.
DURATION OF PARTICIPANT PARTICIPATION AND DURATION OF STUDY	Participants will participate in the study for up to 45 days. The total duration of the study is expected to be 6 months (4.5 months for participant recruitment and 1.5 months for final participant follow-up).
CONCOMMITANT MEDICATIONS	No medications will be restricted as part of this study.
EFFICACY EVALUATIONS	
 Sensation of stimulation experienced by the patient Number of days taken to wean

	
 • Time spent breathing without mechanical ventilation support • Respiratory muscle strength • Peak expiratory flow • Resting breathing parameters
PRIMARY ENDPOINT	
 • Maximum inspiratory and expiratory pressure
SECONDARY ENDPOINTS	
 • Thickness of the abdominal wall muscles • Thickness of the diaphragm • Weaning success • Number of days taken to wean • Time spent breathing without mechanical ventilation support • Cough peak flow • Resting breathing parameters • Adherence to the study protocol • Sensation of stimulation experienced by the patient • Adverse events
STATISTICS Analysis Plan	
Only participants who fulfil the protocol in terms of eligibility, interventions and outcome assessment will be included in the statistical analysis.
 
Study results will first undergo descriptive level statistical analyses. In the second level of analysis, we will quantify the magnitude to which abdominal NMES exhibits a protective effect using regression models.
 
Weaning success will be compared between the study groups using Poisson regression. Kaplan Meier survival analysis will be used to compare the time to wean in both study groups.
 
Adverse event rates will be coded by body system and MedDra classification term. Adverse events will be tabulated by treatment group and will include the number of patients for whom the event occurred, the rate of occurrence, and the severity and relationship to study treatment.

Rationale for Number of Participants	
This study is intended to be a pilot study that will be used to obtain initial data on the feasibility and safety of VentFree to assist in the process of ventilator weaning. The primary outcome of this study is the effect of abdominal NMES on respiratory muscle strength over time. There is currently no data in the literature to support a sample size calculation for this study. Given this constraint, in this pilot study a total of 24 participants was deemed adequate and is consistent with sample size recommendations in the literature.¹ Allowing for a 10% drop out rate, a total of 26 participants will be recruited for this study. The data collected on the secondary endpoints will be used to

	determine the participants needed for a future randomized controlled trial of the device on weaning outcome.
--	--------------------------------------------------------------------------------------------------------------

3 Background

Approximately one million patients in the US are estimated to undergo mechanical ventilation from respiratory failure (MV) every year, resulting in an annual cost of \$27 billion.² Approximately seven hundred thousand of these patients have difficulty weaning from MV, with many requiring prolonged MV.³ In the US, the overall health-care cost of this latter group of patients is estimated to be more than \$16 billion per year.⁴ Furthermore, patients requiring prolonged MV are susceptible to a wide range of secondary complications and have excess mortality.^{5,6} The current standard of care to wean patients requiring prolonged MV is to have them undergo daily spontaneous breathing trials (SBTs).^{7,8} These trials are carried out using a variety of strategies intended to progressively reduce the extent of MV support,^{7,8} while encouraging the patient to breathe on their own. These SBTs, which can last anywhere between days⁵ and months,^{7,8} aim to recondition the respiratory muscles, which are weakened during MV.⁹ However, in the most severe cases, patients may never wean from MV.¹⁰ There are currently only a limited number of interventions that can accelerate the process of weaning from MV.

3.1 The Healthcare Problem

The most common indications for MV, as derived from a study of more than 5000 patients in 20 countries,¹¹ are acute respiratory failure (69%), coma (17%), acute exacerbation of Chronic Obstructive Pulmonary Disease (COPD; 10%), asthma (2%), and neuromuscular disorders (2%). The objectives of MV are to improve gas exchange, relieve respiratory distress and permit lung and airway healing while avoiding complications.¹² Though potentially life-saving, MV can also cause life-threatening complications including barotrauma, ventilator associated pneumonia (VAP), respiratory muscle atrophy, ventilator-associated lung injury and psychological complications such as depression.¹² Accordingly, it is imperative to wean patients from MV in the fastest time possible.¹²

3.2 Why Do Patients Fail To Wean?

In most patients, the primary pathophysiologic mechanism of weaning failure is an imbalance between an excessive respiratory load and reduced respiratory muscle strength (see [Figure 1](#)).¹³ Increased respiratory load can be caused by an increase in the stiffness and/or resistance of the respiratory system.¹² Increased stiffness can be the result of VAP, pulmonary edema and pulmonary fibrosis and increased resistance can be the result of endobronchial neoplastic pathologies, asthma and COPD, or by the process of weaning itself (either by the presence of the endotracheal tube or due to increased secretions following extubation).¹³ Reduced respiratory muscle strength can result from a combination of disuse atrophy/dysfunction, sepsis, polyneuropathy, as well as poor nutrition and medications.¹³ Strikingly, recent evidence has shown a 50% decrease in diaphragm muscle fiber cross sectional area after just 18 to 72 hours of controlled MV.¹⁴

[figure not shown]

Figure 1 Illustration of the imbalance between an excessive respiratory load and reduced respiratory muscle strength

3.3 Current Standard of Care

A recent international symposium generated guidelines for weaning from MV. These guidelines state that active weaning from MV should commence when the pathology responsible for the institution of MV has been resolved and when the patients are clinically stable.¹³ A weaning trial commonly consists of a period of completely unsupported breathing (e.g., T-tube trial) or a period of minimal ventilator support (e.g., pressure support ventilation). If the patient does well during the weaning trial (i.e. is able to comfortably breathe unassisted) he/she is extubated; otherwise, the patient resumes MV.¹³

When patients do not pass the first weaning trial, the potential mechanisms for weaning failure must be identified and addressed.¹³ In addition, the aforementioned guidelines suggest implementing daily SBTs, during which the work of breathing accomplished by the ventilator is progressively reduced, and thus, the respiratory muscles weakened during the preceding pre-weaning period of MV are reconditioned.^{9,15}

3.4 Unmet Medical Need

To date, a daily SBT is the only intervention used in the weaning of prolonged MV patients. Unfortunately, this process can last anywhere between days⁵ and months.^{7,8} In the most severe cases, patients never wean from MV.¹⁰ Therefore, novel interventions designed to hasten the weaning process are sorely needed. This is particularly true for patients requiring long-term MV due to their significant healthcare costs and increased risk of morbidity and mortality.^{4–6}

4 VentFree

VentFree (Liberate Medical, LLC) is a neuromuscular electrical stimulation (NMES) device that applies transcutaneous electrical stimulation to the abdominal wall muscles (primarily rectus abdominis and external oblique) in synchrony with a patient's voluntary exhalation.

NMES elicits muscle contractions through the delivery of small electrical pulses to motor nerves that supply a given muscle.¹⁶ When NMES is applied to the abdominal wall muscles in synchrony with exhalation, the effect on ventilation is similar to a physiological contraction of the muscles.¹⁷ An important advantage of VentFree, however, is that it can be used to recruit the abdominal wall muscles in the absence of patients' voluntary or automatic recruitment of these muscles (i.e. severe atrophy or paralysis). Accordingly, the VentFree technology provides a convenient and consistent method of producing contractions of the abdominal wall muscles for training/strengthening purposes.

4.1 Study Device

This study will use the VentFree prototype (model number: VF03-K) that consists of a commercially available and FDA cleared neuro muscular electrical stimulator (Continuum, Empi, USA) and a stimulation trigger (designed by Liberate Medical). The disposable components of the device are single patient use and include two sets of 4 cm by 5 cm rectangular stimulation electrodes (PALS Platinum) and a variable orifice pneumotachograph (Braebon). A picture of the device is shown in **Error!**

[figure not shown]

Figure 2 VentFree picture
Reference source not found..

The main features of the device are:

- **Exhalation synchronized stimulation to the abdominal wall muscles –** the device allows the timing and duration of the stimulation burst as well as the parameters of the stimulation pulses to be modified by the user.

- **Expiratory flow limitation test** – this mode of the device records the output of the respiratory sensor for the purposes of conducting an expiratory flow limitation test (see Section 11.8).
- **Compliance monitoring** – the time, date and the duration of each stimulation session is recorded by the device.

4.2 Overview of Clinical Studies

A detailed description of the clinical effects of VentFree is included in the Investigators Brochure. This includes the results from: (1) a structured literature review that evaluated the safety and performance of the effect of abdominal muscle stimulation on respiratory function; (2) four prospective clinical trials of VentFree, which collectively included a total of 52 subjects; and (3) a structured review of muscle stimulation adverse events reported to the Food and Drug Administration, Manufacturer and User Facility Device Experience (MAUDE) database. The main findings from this work includes:

1. AFES in synchrony with exhalation can be used to both acutely improve respiratory function, whereby the user's respiratory function is temporarily improved when they are using the device, and to chronically improve respiratory function, whereby a training intervention of the device results in an improvement in the patient's unassisted respiratory function.
2. Fourteen articles, two Ph.D. theses and all four of Liberate Medical's prospective clinical trials supported the acute effects of AFES. This research showed that during AFES-assisted, compared with unassisted, resting breathing tidal volume and minute ventilation were augmented in healthy subjects, patients with COPD, and patients receiving prolonged MV. In addition, Liberate Medical's trials demonstrated that the AFES-induced augmentation in minute ventilation during resting breathing was associated with a reduction in the inspiratory work of breathing. Lastly, studies in the literature demonstrated that AFES could be used to augment cough peak flow in patients with spinal cord injury.
3. Six articles and two Ph.D. theses investigated the chronic (training) effect of AFES. The majority of these studies included patients with spinal cord injury and they all found that FVC, FEV1 and PEF increased in response to AFES training. Three studies included a follow up period, which ranged from 3 months to 6 months. While these studies indicated that the improvement in respiratory function was maintained after training ceased, the long-term effect of AFES remains to be established.

A small number of adverse events were reported in the literature. These were minor, infrequent and transient in nature. No adverse events have been reported in Liberate Medical clinical studies conducted to date. The FDA MAUDE database included reports of injuries and malfunctions resulting from electrical stimulation devices. The reported adverse events were minor in nature, and no further complications were reported. Based on the available safety information, AFES offers an acceptable safety profile.

The combined results from the prospective clinical trials conducted by Liberate Medical and the literature included in the structured literature review have demonstrated that abdominal stimulation applied in synchrony with exhalation can be used to acutely improve breathing volumes in a range of different patient groups. In addition the studies cited in the literature review indicate that abdominal muscle training using electrical stimulation can be used to improve unassisted respiratory function in SCI and that this improvement is sustained after the cessation of stimulation training. Finally, two studies indicate that abdominal stimulation may be able to be used to assist ventilator weaning. However, additional studies are required to verify the abdominal muscle training results in additional patient groups and to determine the functional benefit of abdominal stimulation for patients.

5 Objectives of the Clinical Investigation

The primary objective of this study is to determine whether NMES applied to the abdominal wall muscles in synchrony with exhalation can increase the strength of the respiratory muscles in prolonged mechanical ventilation patients. If feasible it will be used to design a follow up trial on clinically relevant endpoints.

The secondary objectives of the study is to evaluate whether this intervention also affects: (1) the thickness of the abdominal wall muscles and the diaphragm, (2) functional respiratory measurements, and (3) weaning outcome.

6 Study Design

This is a single center, participant blinded randomized placebo-controlled pilot trial that includes 12 patients in the intervention arm and 12 patients in the placebo arm.

Screening data will be reviewed to determine participant eligibility. Patients who meet all of the inclusion criteria and none of the exclusion criteria and who are willing to participate in the study will be entered into the investigation.

Each participant will receive either active or placebo electrical muscle stimulation to the abdominal wall during exhalation for sixty minutes per day, five days per week for the shorter of six weeks or until the patient is weaned from mechanical ventilation. Participants will be assigned to active or placebo stimulation in random order (using a random number generator). Evaluations will be performed at baseline, after three weeks of treatment and at the end of treatment. A flow diagram of the study protocol is shown in Figure 3

[figure not shown]

Figure 3 Study Flow Diagram

The maximum duration of participant participation is 45 days. The total duration of the study is expected to be 6 months.

7 Outcome Measures

7.1 Primary Outcome Measures

The primary outcome measure in this study is:

- **Maximum Expiratory and Inspiratory Pressure** – The strength of the inspiratory and expiratory muscles will be assessed using the maximum inspiratory pressure and maximum expiratory pressure test respectively.

7.2 Secondary Outcome Measures

The secondary outcome measures in this study are:

- **Thickness of the Abdominal Wall Muscles** – The end inspiratory and end expiratory thickness of the external oblique, internal oblique and transversus abdominis muscles will be measured using ultrasound.
- **Thickness of the Diaphragm** - The end inspiratory and end expiratory thickness of the diaphragm will be measured using ultrasound.
- **Weaning Success** – Defined as 72 hours of spontaneous respiration without any mechanical ventilation support.
- **Number of Days Taken to Wean** – Defined as the time from the patient's original admission to the point of weaning success.
- **Time spent breathing without mechanical ventilation support** - The time spent breathing without MV support will be recorded on a daily basis throughout the study.
- **Cough Peak Flow** – The peak flow during a voluntary cough will be recorded.
- **Resting Breathing** – This outcome will be assessed using measurements of tidal volume, respiratory rate and minute ventilation during a one-minute period of resting breathing.
- **Adherence to the Weaning Protocol** – The number and duration of the weaning sessions supported by electrical stimulation during the study period will be recorded for each participant.
- **Sensation of Stimulation Experienced by the Patient** – Surface electrical muscle stimulation stimulates sensory nerves in addition to motor nerves and can cause pain at high intensities. The degree of discomfort experienced by participants during stimulation will be quantified using the behavioral pain scale.¹⁸
- **Adverse Events** – All medical complications experienced by the study participants during the study will be assessed for severity and relationship to the study device and recorded.

8 Participant Selection

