8.2 Inclusion Criteria

- Patients who have been mechanically ventilated for more than fourteen days.
- Clinically stable: oxygen saturation > 90% with a fractional inspired oxygen ≤ 0.40, external PEEP ≤ 5 cm H₂O, temperature ranging from 35.5 to 38.5°C, no intravenous administration of vasoactive agents.

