12.6 Early Withdrawal Visit

In the case that the patient withdraws or is withdrawn from the protocol (see Section 14) before the end of the intervention period, and providing the patient consents, then the investigators will perform and record the participant's MEP, MIP, thickness of the abdominal wall muscles and diaphragm, CPF, resting breathing parameters and adverse events related to stimulation or otherwise.

If the participant is withdrawn from the study because they have successfully weaned from mechanical ventilation then the study researcher will also calculate and record the number of days taken to wean taken from the institution of mechanical ventilation.

13 Adverse Experience Reporting and Documentation

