12.3 Replacement of Participants

While it is estimated that 24 is a suitable sample size for this study, the actual study sample size of 26 allows for a 10% drop out rate. Therefore, up to two participants who withdraw from the study will be replaced.

15 Protocol Violations

A protocol violation occurs when the participant, investigator, or Sponsor fails to adhere to significant protocol requirements affecting the inclusion, exclusion, participant safety and primary endpoint criteria.

Failure to comply with Good Clinical Practice (GCP) guidelines will also result in a protocol violation. The Sponsor will determine if a protocol violation will result in withdrawal of a participant.

When a protocol violation occurs, it will be discussed with the investigator and a Protocol Violation Form detailing the violation will be generated. This form will be signed by a Sponsor representative and the Investigator. A copy of the form will be filed in the site's regulatory binder and in the Sponsor's files.

16 Protocol Amendments

Amendments to the clinical investigation plan must be submitted to the Sponsor for review before submitting to the appropriate IRB for approval.

17 Statistical Methods and Considerations

Only participants who fulfil the protocol in terms of eligibility, interventions and outcome assessment will be included in the statistical analysis. Patient variables will be presented using means and standard deviations for continuous normally distributed variables, medians and interquartile ranges for continuous non-normally distributed variables, and proportions and absolute numbers for categorical variables.

Adverse event rates will be coded by body system and MedDra classification term. Adverse events will be tabulated by treatment group and will include the number of patients for whom the event occurred, the rate of occurrence, and the severity and relationship to study treatment.

Study results will first undergo descriptive level statistical analyses. For continuous variables, Two-way, Student's t-tests will then be carried out using unequal variances where the variables are normally distributed. Tests for normality will be carried out using the Shapiro-Wilk method. Variables that are not normal in distribution that also cannot be log transformed to a normal distribution curve will be analysed using the Mann-Whitney U test or other non-parametric methods to be determined based on actual data distributions.

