In the second level of analysis, we will quantify the magnitude to which abdominal NMES exhibits a protective effect. Crude and adjusted linear regression models will be carried out where the outcome variable is continuous and the covariates are normally distributed or categorical. Our prior experience with measures of respiratory function, which will be measured in this study, indicate that select covariates may need to be controlled for or otherwise do not always fit a normal distribution. Therefore, crude and adjusted generalized linear models are anticipated. These regression models will be carried out at the point of successful wean. All multiple regression covariates, linear or generalized, will be assessed for interaction, collinearity and confounding. For all unadjusted and adjusted multinomial models the overall model log likelihood ratio and Hosmer and Lameshow goodness-of-fit will be conducted to ensure models report significance and are not over fitted. Adjusted regression models will undergo sensitivity analysis and bootstrap analyses. Bootstrap analysis is a re-sampling strategy to estimate the population parameter of interest based on the observed, sample data.

The number of tries to successful wean will be quantified using Poisson regression. Crude and adjusted models will be carried out. Kaplan-Meier survival analysis will be carried out to quantify differences in the time to wean in the treatment abdominal NMES modality compared to the control. As the patients will be resident in hospital facilities, we do not anticipate significant methodological concerns with respect to censoring.

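### Days to wean is defined from admission but recorded from the start of ventilation; neither clock starts at randomisation, and death before weaning has no analysis rule

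*Combined protocol and SAP*

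**What the plan says.** - **Definition.** Section 7.2 defines days to wean as running from "original admission to the point of weaning success". It does not say whether this means the hospital, the intensive care unit or a weaning facility.
- **Recording.** Section 12.6 tells the researcher, for a participant who leaves because of successful weaning, to record the "number of days taken to wean taken from the institution of mechanical ventilation". Appendix A schedules this item only in the Early Withdrawal column, so Section 12.6 is the only recording instruction.
- **Entry.** The synopsis admits "Patients who have been mechanically ventilated for at least fourteen days"; Section 8.2 has "Patients who have been mechanically ventilated for more than fourteen days". Randomisation is on Day 1, after consent and the eligibility check (Section 12.1).
- **Analysis.** The synopsis states that "Kaplan Meier survival analysis will be used to compare the time to wean in both study groups". Section 17 repeats the plan. Neither gives a time origin or mentions delayed entry.
- **Censoring and death.** Section 17 says that, because patients are in hospital, "we do not anticipate significant methodological concerns with respect to censoring". Death appears as a serious adverse event outcome (Section 13.2) and, if expected within four weeks, as an exclusion (Section 8.3). It is not among the possible discontinuation reasons listed in Section 14.1.
- **Analysis set.** The synopsis and Section 17 both state: "Only participants who fulfil the protocol in terms of eligibility, interventions and outcome assessment will be included in the statistical analysis".

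**The concern.** The endpoint has two incompatible starting points, and the one that staff are told to record is not the one that defines the outcome. Both most naturally lie before randomisation. A participant must still be ventilated to enter, so none can reach the weaning event in that earlier stretch. If it is added to each survival time, participants are compared at different distances from the start of treatment.

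Death is a separate gap. Hospital residence answers loss to follow-up, but it does not say what happens to a participant who dies unweaned. Such a participant could be censored, kept as never weaned, or left out for incomplete outcome assessment, and each choice can give a different answer.

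The stake is mainly the next trial. Section 17.1 says that the secondary-endpoint data will be used to size a trial on weaning outcome. That trial will need time from start of treatment, and neither stated clock measures it.

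**Working it through.** The plan gives no figure for this endpoint, so there is nothing to reproduce. The contradiction rests on the text; the arithmetic below only shows what could follow from it.

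**1. Do the two clocks agree?** Days from admission = days from ventilation start + (ventilation start − admission). They are equal only when the bracket is zero, that is, when ventilation began on the day of admission.

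**2. How much of the ventilation clock precedes randomisation?** Taking the 14-day minimum, the share for a participant weaned *d* days after Day 1 is 14/(14 + *d*):

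- *d* = 10: 14/24 = 58%
- *d* = 20: 14/34 = 41%
- *d* = 30: 14/44 = 32%
- *d* = 44: 14/58 = 24%

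If every participant had the same pre-randomisation time, all times would shift equally and a rank-based comparison would not change. Only the spread matters.

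**3. Chance imbalance between arms.** Section 6 gives "12 patients in the intervention arm and 12 patients in the placebo arm". The 95% range for the difference in mean pre-randomisation time is ±1.96 × SD × √(2/12). The SD is not in the documents. Assuming 5, 10 or 20 days gives ±4.0, ±8.0 or ±16.0 days. The expected difference is zero because randomisation comes afterwards.

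**4. Illustrative effect on power.** All of these inputs are assumptions: 12 per arm, exponential weaning times, censoring 44 days after Day 1, a two-sided 5% log-rank test (the plan names no test), and pre-randomisation time of 14 days plus an exponential excess with the SD shown. There were 10,000 simulated trials per setting, with Monte Carlo standard error at most 0.5 points.

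| Hazard ratio, control median | SD (days) | From randomisation | Ventilation clock | Ventilation clock, delayed entry |
|---|---|---|---|---|
| 3, 15 days | 5 | 69.6% | 62.4% | 69.2% |
| 3, 15 days | 10 | 70.2% | 48.4% | 67.8% |
| 3, 15 days | 20 | 70.5% | 30.1% | 64.2% |
| 2, 30 days | 5 | 30.9% | 29.8% | 30.6% |
| 2, 30 days | 10 | 31.7% | 27.3% | 30.3% |
| 2, 30 days | 20 | 32.1% | 22.9% | 28.9% |

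With no treatment effect, rejection was 5.2% to 6.2% on every clock. At SD 0 the three clocks agree.

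**5. Death rule.** Take an invented arm of 12 with 6 weaned, 2 dead unweaned and 4 alive unweaned at the end.

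- Deaths kept as unweaned: 6/12 = 50%.
- Deaths dropped: 6/10 = 60%.
- Deaths censored (one minus Kaplan-Meier): both before any weaning, 1 − 4/10 = 60%; both after the third weaning, 1 − (9/12)(4/7) = 57.1%; both after all weanings, 1 − 6/12 = 50%.

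**The case against.** The strongest reply is that the plan is sound enough in practice. Staff have one recording instruction, so a reader who inferred that two staff members would record different values for the same participant would be wrong. The mismatch is between the definition and the recorded value. Time without ventilator support is also recorded daily and scheduled at every visit from baseline, so time from Day 1 can be rebuilt. The endpoint is secondary in a pilot that makes no power claim. All of this stands, and it is why the severity is low.

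Other stronger readings also fail:

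- **That the Kaplan-Meier analysis is stated to run from admission.** Section 17 does not cite Section 7.2. The link is an inference, drawn because Sections 7.2 and 12.6 contain the only definitions.
- **That admission certainly precedes Day 1 by 14 days.** The 14-day minimum applies to ventilation. Admission most naturally comes earlier than Day 1, but the facility is undefined.
- **That the comparison is biased or type I error inflated.** Pre-randomisation time is balanced in expectation, and null rejection is the same on each clock.
- **That a large loss of power has been shown.** The documents give no spread, weaning rate or hazard ratio. At hazard ratio 2 and SD 5 the loss is 1 to 3 points.
- **That the plan drops deaths.** The analysis-set sentence does not mention death; dropping them is one possible reading.
- **That participants alive and unweaned at the end are unhandled.** Kaplan-Meier censors them by default.

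What remains is the contradiction, the missing origin and the missing death rule.

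**Conclusion.** The point holds at low severity and is worth fixing. Three parts rest on the text alone: the defined and recorded clocks differ, Section 17 states no origin or delayed entry, and no rule covers death before weaning. That pre-randomisation time would enter the comparison depends on one inference, namely that the analysis uses one of the two stated clocks.

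If it does, the harm is noise that grows with the spread of time before entry. Under the assumptions shown, the loss ranges from about 1 point to about 40 points of power (70.5% to 30.1%), and it is near zero if participants enter soon after day 14. These figures are illustrations, not estimates for this trial. The gap of 50% against 60% is likewise conditional on deaths being dropped and on the invented counts.

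**What to change.** Use one definition in Sections 7.2, 12.6 and 17, with a matching change in the synopsis:

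> Time to wean is the number of days from randomisation (Day 1) to weaning success. All randomised participants are included in this analysis, including any who are later replaced; the set fulfilling the protocol is a sensitivity analysis. Participants alive and unweaned are censored at their Final Visit or, if withdrawn, at the last day with known ventilation status. Death before weaning is a competing event, and the cumulative incidence of weaning is reported by arm (Aalen-Johansen estimator). A death after withdrawal and after the last known ventilation status leaves the participant censored at that last day.

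A simpler alternative keeps known deaths in the risk set as unweaned to Day 47, the latest permitted Final Visit, and reads the proportion weaned from one minus Kaplan-Meier. This is only approximate when some participants are censored early.

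Report days from admission (with the facility named) and from ventilation start descriptively. If either is compared between arms, use delayed entry at randomisation.

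The cost is wording, including one exception to the analysis-set sentence. No new measurement is needed: Day 1 is known, ventilator-free time is recorded daily, and deaths are captured as serious adverse events. There are two downsides. The headline time is no longer total ventilation duration, and including everyone randomised may dilute the effect through participants who received little stimulation.
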